6 prompt the patient when they ‘break a movement rule’ that has been programmed for them by
7 the clinician. Individualised movement ‘prompts’ may be time-based, such as reducing long
8 periods of sitting without getting up and moving, or may be kinematically-based, such as
9 reducing sitting in an excessively upright position.

10
11 There is no provision for trial-funded ancillary or post-trial care.

12 13 **Clinician recruitment and training**

14 Depending on recruitment and training success, approximately 16 physiotherapists (8 in each
15 city) will deliver the interventions at private physiotherapy clinics. Each physiotherapist will
16 deliver only one CFT treatment arm, to prevent learning (contamination) from experience
17 using the movement sensor output being applied to the CFT-only patients. Physiotherapists
18 will be randomised into either the CFT-only group or CFT-plus-movement-sensor-
19 biofeedback group. Up to four additional physiotherapists will be recruited and trained in
20 each city to act as reserves if required. For physiotherapists to be considered for inclusion in
21 the training program, they will need to have: at least 2 years clinical experience post-
22 graduation; experience treating people with chronic LBP; an interest in applying
23 biopsychosocial management principles via CFT; a willingness to use movement sensors
24 clinically; less than 4 days of prior exposure to CFT training; and a willingness to be

1
2
3 1 observed and videoed for mentoring and feedback purposes while treating a *non-trial* patient
4
5 2 with disabling LBP.
6
7
8 3

9
10 4 The clinician training for both the CFT-only group and CFT-plus-movement-sensor-
11
12 5 biofeedback group will consist of three components: (i) clinical workshops including live
13
14 6 patient demonstrations and mentoring of the physiotherapists while treating patients, (ii)
15
16 7 online resources (e.g. e-book and training videos) and (iii) Facebook private support group
17
18 8 pages.
19
20
21 9

22 23 24 10 *CFT training*

25
26 11 Six clinical workshops will be conducted (a two-day workshop every month for 6 months) in
27
28 12 each city where both CFT-only and CFT-plus-movement-sensor-biofeedback groups will
29
30 13 train together. A final single day workshop will be held for each group separately when
31
32 14 clinicians will need to demonstrate a pre-defined level of competency, as evaluated by the
33
34 15 CFT and movement sensor clinical trainers using a structured competency check-list, before
35
36 16 being eligible to deliver the relevant intervention in the trial. The training workshops will
37
38 17 include an initial introductory workshop about CFT with patient involvement, a workshop to
39
40 18 build skills regarding communication and behavioural experiments, and four workshops
41
42 19 involving observation of each physiotherapist examining and treating people with disabling
43
44 20 LBP using CFT. The later four sessions will be observed by the clinical trainers, who will
45
46 21 provide personalised feedback using a competency checklist developed for the training. The
47
48 22 CFT training will be conducted by physiotherapists (POS and JPC) who developed the CFT
49
50 23 approach and have extensive experience using and teaching CFT. Clinical competency will
51
52 24 be assessed in a final one-day workshop, or by ongoing videos of patients if required.
53
54
55
56
57
58
59
60

1 *Movement sensor training*

2
3 Because the ViMove2 movement sensors are worn by participants in both CFT groups, all
4
5 participating clinicians will attend a 2-hour technical workshop on setting up and using the
6
7 ViMove2 devices. This workshop will focus on sensor placement, how to test they are
8
9 working and how to troubleshoot technical issues. The training will occur after the 6th
10
11 training workshop and at least 2 weeks before the final single-day workshop. The clinicians
12
13 in the CFT-plus-movement-sensor-biofeedback group will attend a second 4-hour workshop
14
15 on accessing and interpreting the movement data (kinematic and EMG) and programming
16
17 biofeedback. These movement sensor workshops will be conducted by a physiotherapist (RL)
18
19 with extensive experience using these movement sensors clinically and teaching clinicians in
20
21 their use. Personalised mentoring by RL will be available over the phone to each
22
23 physiotherapist for up to five post-hoc reviews of treatment sessions of trial participants.
24
25
26
27
28
29
30
31
32

33 *Ongoing support for both clinician groups*

34
35 During the trial, private Facebook pages (one on CFT, one on movement sensors for the
36
37 CFT-only group and one on movement sensors for the CFT-plus-movement-sensor-
38
39 biofeedback group) and 3-monthly virtual or face-to-face meetings with a clinical trainer will
40
41 be provided for both clinician groups separately to provide a forum for the discussion of
42
43 challenges faced when implementing the intervention or with technical issues related to the
44
45 sensors. The trainers will contribute to the Facebook discussion and 3-monthly meetings.
46
47
48
49
50

51 *Treatment fidelity checking*

52
53 Every seventh participant of each clinician will be selected, and their treatment monitored by
54
55 the appropriate clinician trainer to ensure ongoing treatment fidelity. If the seventh
56
57 participant does not consent to this occurring, each subsequent participant of that clinician
58
59
60

1 will be asked until one consents. This process is recommended in the Spillane (2007)²⁷
2 framework for implementation fidelity in trials. This will take the form of video recordings of
3 three consultations (a consultation early in the treatment process, one in the middle and one
4 close to the end of the treatment period) that will be reviewed by a randomly selected
5 clinician trainer (POS, JPC or KOS) with brief feedback provided if required.

7 **Data collection and outcome measures**

8 Data collection will occur at baseline, and at 3, 6, 13, 26, 40 and 52 weeks. Where ever
9 possible, all data will be completed on-line directly into the trial database. Alternatively,
10 patients can complete follow ups over the telephone with a researcher. If participants do not
11 complete follow-ups within 2 day of the scheduled date, they will receive an email reminder
12 and then 2 days later will be contacted by one of the study team. Data collected via the ViMove
13 sensors at each clinical visit will be directly uploaded to a database. A detailed description of
14 the data collected at each time point is presented in Table 1.

16 *Primary outcomes*

17 The primary clinical outcome will be pain-related physical activity limitation measured using
18 the Roland Morris Disability Questionnaire^{28 29} (RMDQ). For the economic efficiency (cost-
19 utility) analysis, the primary outcome of clinical effect will be quality-adjusted life years
20 calculated using the area under the curve approach based on responses to the EQ-5D-5L
21 questionnaire³⁰ across each of the assessment time points.

23 *Secondary outcomes*

24 The secondary outcomes include:

- 25 • Pain intensity (three numeric rating scales)³¹

- 1 • Patient-specific activity limitation (Patient-Specific Functional Scale)³²
- 2 • Pain catastrophisation (Pain Catastrophizing Scale)³³
- 3 • Pain self-efficacy (Pain Self-efficacy Questionnaire)³⁴
- 4 • Fear of movement (physical activity subscale of the Fear Avoidance Beliefs Questionnaire)³⁵
- 6 • Patient-perceived global improvement (1 question)³⁶
- 7 • Patient satisfaction with care and treatment (1 question)³⁷
- 8 • Adverse events (defined as any morbidity or events causing unwarranted distress to a participant that were potentially related to any trial-related intervention). Clinicians and follow-up questionnaires will inquire about any adverse events.
- 11 • Lumbosacral movement will be measured in both CFT treatment groups using ViMove2 wearable wireless sensors and used in the mediation analysis.
- 13 • Direct health costs attributable to consumption of health care resources (measured using extracts from Medicare and Pharmaceutical Benefits databases and direct patient reports) and productivity costs (measured using the iMTA Productivity Cost Questionnaire³⁸).

17 **Sample size calculation**

18 The sample size was calculated for the primary outcome using the program STATA. A total
19 of 492 patients (164 per group) will be recruited to detect a difference of 2 points (0-24 scale)
20 on the RMDQ between the CFT-only group and CFT-plus-movement-sensor-biofeedback
21 group, $p < 0.05$, 80% power, a common standard deviation of 6 points and a worst-case
22 scenario of 20% drop-out rate. Based on our pilot study results^{20 39}, we hypothesise that the
23 CFT-plus-movement-sensor-biofeedback group would have an average score of 7.5 points on
24 the RMDQ and the Usual care group would have a score of 11.5 points. Pragmatically and
25 arbitrarily, we assume the CFT-only group will have a mean outcome that is half-way (9.5)

1 between the other two groups and so we will power the trial to detect this as the smallest
2 likely between-group difference ($11.5-9.5=2.0$).

4 **Blinding**

5 Patients will not be informed of any anticipated results of the trial and will be told that the
6 trial is comparing usual care to two evidence-based interventions. All outcome measures will
7 be either self-reported by patients via web-based questionnaires or collected via the
8 movement sensors or MBS/PBS registers. Unblinded clinicians will deliver only type of one
9 treatment and play no role in collecting data, other than performing a standardised movement
10 protocol with the resultant movement data being automatically uploaded by the sensors to a
11 server without clinician input. Statisticians will be blind to groups.

13 **Statistical analysis**

14 Almost all participant-reported data will be entered directly into an electronic database,
15 where range values are automatically checked. In addition, all data will be checked for range
16 values and outliers prior to analysis.

18 *Treatment efficacy analysis*

19 Repeated-measure linear mixed models will be used to assess the effect of treatment on pain-
20 related physical activity limitation across all time points (3, 6, 13, 26, 40 and 52 weeks), with
21 the primary comparison being a formal test of adjusted mean differences between groups at
22 13 weeks using intention-to-treat principles. Appropriate sensitivity analyses will be
23 performed on multiple imputed datasets. Estimates of treatment effect will be adjusted for
24 baseline scores of symptom duration, pain intensity, activity limitation (RMDQ score),
25 treatment expectations and significant clinician cluster effects.

1
2
3 1 The secondary outcome measures will be evaluated using the equivalent repeated-measure
4
5 2 linear mixed models.
6
7
8 3

9
10 4 As widely recommended, we will focus on reporting the size of the effect and its uncertainty
11
12 5 (including describing compatibility intervals and p-values) rather than making judgements
13
14 6 based on an arbitrary p-value threshold⁴⁰⁻⁴². In the papers that report the outcomes of this
15
16 7 clinical trial, effect sizes will be discussed relative to those obtained by other interventions in
17
18 8 comparable populations.
19
20
21 9

22 23 24 10 *Analysis of economic efficiency*

25
26 11 Direct healthcare and indirect (productivity) costs incurred by participants will be measured
27
28 12 over the 12-month follow-up period. Direct health costs will be collected using Medicare
29
30 13 Benefits Scheme (MBS) and Pharmaceutical Benefits Scheme (PBS) database extractions,
31
32 14 and patient questionnaires to capture other health care costs (e.g. hospitalisations). Indirect
33
34 15 health costs (e.g. travel to appointments) and productivity costs (including absenteeism and
35
36 16 presenteeism) will also be captured in the 3-monthly patient questionnaires. Productivity
37
38 17 costs will be measured using the 'iMTA Productivity Cost Questionnaire'. Productivity costs
39
40 18 measured at specific time points will be extrapolated to the full one-year period using an area
41
42 19 under the curve approach. All costs will be calculated using a 2019-2020 financial base year.
43
44 20 Hospital costs will be valued using the National Weighted Activity Unit calculators for the
45
46 21 2019-2020 year.
47
48
49
50
51 22

52
53 23 An incremental cost-utility analysis will calculate the difference in costs between intervention
54
55 24 and control groups divided by the difference in quality-adjusted life years. Incremental cost-
56
57 25 utility analyses will be undertaken from societal (primary analysis) and health service
58
59
60

1 (secondary analysis) perspectives. There will also be analyses undertaken for valuation of
2 productivity costs using human capital (primary analysis) and friction (secondary analysis)
3 methods. Bootstrap resampling (2000 replications of original sample size) will be used to
4 generate a 95% confidence ellipse surrounding the incremental cost-utility estimate. Cost-
5 effectiveness acceptability curve analyses will be undertaken if the intervention is not found
6 to dominate the control condition.

7 8 Moderation analysis

9 To investigate if treatment effect is moderated by cognitive flexibility, baseline activity
10 limitation, baseline pain, catastrophisation or self-efficacy (all groups), the interaction term
11 between the potential moderator and the treatment group variable will be assessed in the
12 repeated-measure linear mixed models for pain-related activity limitation and pain intensity
13 described above. Only in the CFT groups, similar moderation analysis will also occur using
14 the STaRT MSK Tool^{43 44} (measured at baseline), therapeutic alliance⁴⁵ (measured at 3
15 weeks) and participant-rated adherence to the treatment program measured at weeks 3, 6 and
16 12 with a study-specific single question ('How would you rate your adherence to the
17 treatment program your physiotherapist has recommended?' 0-10 no adherence to complete
18 adherence).

19 20 Mediation analysis

21 To investigate whether improvement in patients' activity limitation was mediated by
22 correction of habituated functional movement behaviors, or changing patient's pain-related
23 cognitions and emotions, a multilevel structural equation model framework will be utilised.
24 Investigation of the mediation roles of cognitions and emotions will occur using data from all
25 patients; whereas, investigation of the mediation roles of change in movement will occur

1 using data from only patients in the CFT groups. Results will be expressed as standardised
2 estimates of mediated treatment effect with bootstrapped 95% confidence intervals.

3
4
5
6
7
8
9
10 **Monitoring:**

11 Because this is not a drug trial and the funder has no access to the data, a data monitoring
12 committee will not be formed and there is no planned trial audit. This does not preclude the
13 administering institution choosing to conduct an audit. There will be no interim analysis and,
14 due to the very low risk of harm, there are no stopping guidelines.

15
16
17
18
19
20
21
22
23
24 **Ethics and dissemination:**

25 This study will be conducted in accordance with the Therapeutic Goods Administration's
26 Note for Guidance on Good Clinical Practice, the NHMRC National Statement on Ethical
27 Conduct in Human Research and the Australian Code for the Responsible Conduct of
28 Research.

29 Authorship will be based on the Vancouver Convention⁴⁶ and no professional writers will be
30 involved.

31 Any protocol amendments will be detailed in the trial registration
32 (ACTRN12618001396213).

33 Metadata and appropriate copies of publications will be deposited in the Curtin University
34 eSpace, which is an open access digital repository.

1 Results will be disseminated via publications in peer-reviewed scientific journals, popular
2 press articles, social media and presentations to scientific and general public audiences.
3
4
5
6
7
8
9

10 **Data sharing**

11 De-identified data and statistical code will be made available on request soon after each
12 report of the data has been published. Different aspects of the data will be published
13 separately, which will determine when those data are publicly available. A data-sharing
14 agreement will require a commitment to using the data only for specified research purposes,
15 to securing the data appropriately and to destroying the data after a nominated period.
16
17
18
19
20
21
22
23
24
25

26 **Acknowledgments**

27 The investigators acknowledge the National Health & Medical Research Council (grant
28 number 1145271).
29
30
31
32
33
34
35
36
37
38
39
40
41
42
43
44
45
46
47
48
49
50
51
52
53
54
55
56
57
58
59
60

References

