6 including patient demographics and outcome measures, via the online database. A researcher
7 will be available by phone if they require assistance. A detailed description of the baseline
8 variables is provided in Table 1.

9 10 **Randomisation**

11 After completing the baseline assessment, dynamic (adaptive) random allocation will be used
12 to randomise participants to treatment groups. Randomisation using a 1:1:1 allocation ratio
13 will be conducted by a research assistant by phoning the NHMRC Clinical Trials Centre (24-
14 hour phone service), thereby ensuring concealment of treatment allocation. The NHMRC
15 Clinical Trials Centre will be blinded to baseline assessment. After randomisation and only
16 for those randomised to the CFT-only and CFT-plus-movement-sensor-biofeedback groups, a
17 research assistant will make an appointment for them with a study clinician at an accessible
18 location in their city.

19 20 **Study treatment**

21 *Group 1: Usual care*

22 This treatment will be the usual care pathway the participant's health providers recommend
23 and/or the participant chooses. Treatment in this group will not be impacted in any way by
24 participation in the study. Participants in this group only will be paid a token reimbursement
25 for their time completing follow-up questionnaires (AU\$30 for the 3-month questionnaire,

1 \$30 for the 12-month questionnaire and an additional \$50 if they complete all the six follow-
2 up questionnaires (3 and 6 week, 3, 6, 9 and 12 month).

3 4 *Commonalities across the two CFT treatment groups (Groups 2 and 3)*

5 Both CFT treatment groups will have the same treatment frequency of seven treatment
6 sessions over 12 weeks plus a 'booster' session at 26 weeks (initial consultation 60 minutes,
7 follow ups 30-40 minutes), in physiotherapy clinics. In both groups, clinicians will use a
8 structured approach to address the relevant cognitive, emotional and behavioural (functional
9 and lifestyle) factors deemed relevant to the individual's presentation¹⁷.

10
11 Based on prior screening (Orebro Musculoskeletal Pain Questionnaire and the Patient-
12 Specific Functional Scale) combined with a comprehensive interview and functional
13 examination, the clinician will identify the multidimensional contributors to pain, distress and
14 disability. This will enable the physiotherapist to design a management plan that is tailored to
15 the person's unique clinical presentation and context.

16

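### The printed inputs give about 77% power with 164 per group, not 80%, and the calculation makes no allowance for therapist clustering

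*Supplement*

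**What the plan says.** All references are to the latest protocol, the revised manuscript.

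- *Sample size calculation*: a total "of 492 patients (164 per group) will be recruited to detect a difference of 2 points (0-24 scale"). The contrast named is "on the RMDQ between the CFT-only group and CFT-plus-movement-sensor-biofeedback". The remaining inputs are a significance level of 0.05, "80% power, a common standard deviation of 6 points and a worst-case" "scenario of 20% drop-out rate". Sidedness is not stated. Nor is it said whether the SD of 6 is raw or residual after baseline adjustment. The section mentions no ICC, design effect or number of therapists.
- *Randomisation*: patients are allocated 1:1:1.
- *Clinician recruitment and training*: "Depending on recruitment and training success, approximately 16 physiotherapists (8 in each" city) deliver the interventions. Each is randomised to one CFT arm and treats only in that arm. Up to four reserves per city may be added.
- *Treatment efficacy analysis*: the models adjust for baseline RMDQ and other baseline variables, and for clinician cluster effects where these are significant. The primary comparison is a formal test between groups at 13 weeks.

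**The concern.** There are two separate problems.

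First, the section prints every input except sidedness, so its figure can be checked, and the usual two-sample formula does not return it. The design does not have the stated power under its own stated assumptions.

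Second, therapist is fully nested within arm in the contrast that the section names. Any variation between therapists adds directly to the variance of the difference between the CFT arms, and only about 16 therapists are available to estimate it. The analysis section allows for clinician effects, but the sample size section does not.

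What is at stake is how an inconclusive sensor result is read. A reader who takes 80% at face value would give a null comparison of the two CFT arms more weight than the design supports.

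**Working it through.** **Inputs.** From *Sample size calculation*: difference 2, SD 6, alpha 0.05 (taken as two-sided), power 80%, drop-out 20%, 164 per group. From *Clinician recruitment and training*: about 16 therapists, taken as 8 per CFT arm (an equal split is an assumption), or 12 per arm if all eight reserves are used. Assumed, because the documents give neither: ICC 0.01 to 0.05; baseline-outcome correlation r = 0 or 0.5.

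**1. Trying to reproduce 164.**

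n per group = 2 × (1.960 + 0.8416)² × 6² / 2² = 141.3, so 142 (143 by the t distribution).

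- Inflated for 20% loss: 142 / 0.8 = 177.5, so 178 per group, or 534 in total (179 and 537 by t).
- Inflated the wrong way: 142 × 1.2 = 170.4, so 171.
- One-sided test: 112 analysable, inflated to 140 (or 135 the wrong way).

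None of these gives 164.

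**2. Power with 164 recruited.**

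- Analysable: 164 × 0.8 = 131.2 per group.
- Standard error: 6 × √(2/131.2) = 0.741, so 2/0.741 = 2.70.
- Power: Φ(2.70 − 1.96) = 0.770 (0.767 by t).
- Difference detectable with 80% power: (1.960 + 0.8416) × 0.741 = 2.08 points.
- Loss at which 80% still holds: 1 − 142/164 = 13.4%.
- With no loss at all, 164 per group gives 85.5%.

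**3. Sensor contrast with therapist clustering.**

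Design effect = 1 + (m − 1) × ICC, where m is completers per therapist: 131.2/8 = 16.4, or 131.2/12 = 10.9. The variance of the difference is multiplied by the design effect. Power is taken from the noncentral t with (therapists − 2) df, or from the normal approximation. For r = 0.5 the SD becomes 6 × √(1 − 0.25) = 5.20, with the ICC applied to the residual variance.

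| Therapists per arm | r | Method | ICC 0.01 | ICC 0.02 | ICC 0.05 |
|---|---|---|---|---|---|
| 8 | 0 | t, 14 df | 65% | 59% | 47% |
| 8 | 0 | normal | 71% | 66% | 53% |
| 12 | 0 | t, 22 df | 69% | 65% | 56% |
| 8 | 0.5 | t, 14 df | 77% | 72% | 59% |
| 8 | 0.5 | normal | 83% | 78% | 65% |

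With 8 per arm the design effects are 1.15, 1.31 and 1.77; with 12 per arm, 1.10, 1.20 and 1.50. The 14-df reference distribution alone, at ICC 0 and r = 0, lowers power from 77% to 71%, so part of the fall in the t rows comes from having few therapists rather than from the design effect.

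**4. Usual care against CFT-only.** This is also a 2-point difference (11.5 − 9.5), with only one arm clustered by study therapist. The standard error is 6 × √((1 + design effect)/131.2). By normal approximation with r = 0, power is 74%, 71% and 63% at ICC 0.01, 0.02 and 0.05. These figures should be compared with the normal rows above, not with the t rows.

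**The case against.** The strongest reply has five parts.

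- **The unclustered shortfall is small.** It is 3 percentage points, or 2.08 detectable points instead of 2.00, and the protocol calls 20% loss a worst case. This stands as to size. But the 80% is stated together with that worst case, and the two do not fit.
- **Baseline adjustment may restore the power.** Without clustering, r of about 0.3 brings power back to about 81%. With r = 0.5 and ICC 0.01 the normal approximation gives 83%. This is a fair possibility, since the analysis does adjust for baseline RMDQ. But the sample size section neither claims this credit nor states a correlation, so a reader cannot rely on it.
- **A flat 47% to 65% overstates what is known.** This stands. A reader might infer that the sensor contrast simply has that power. It follows only if ICC 0.01 to 0.05, 8 therapists per arm, a 14-df test and no baseline credit all hold together. The documents give no ICC, allow for reserve therapists, and do not prespecify a 14-df test, because clinician effects enter only if significant.
- **The protocol does not call the sensor contrast fully powered.** This also stands. A reader might take the phrase in *Strengths and limitations of this study* that way, but there it describes CFT against usual care. For CFT-plus-sensor against usual care the hypothesised difference is 4 points (11.5 − 7.5), and power exceeds 99% even at ICC 0.05 with one arm clustered (normal approximation).
- **Reporting will be based on estimates.** The plan will report effect sizes with intervals rather than judge by a p-value threshold. That lessens the risk of misreading a null result. It does not correct the stated power, and a formal test at 13 weeks remains the primary comparison.

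**Conclusion.** The point holds in two parts of different firmness.

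Firm: under the printed inputs and a two-sided test, 164 per group with 20% loss gives about 77% power. 80% at that loss needs about 178 per group, or a loss of no more than about 13%. No assumption from outside the documents is needed beyond two-sidedness.

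Firm in direction, conditional in size: the sample size makes no allowance for therapist clustering although the design nests therapists in arm. On the printed SD, any positive ICC takes the 2-point contrasts below 77% unless baseline adjustment is credited. For the sensor contrast over ICC 0.01 to 0.05, the range runs from 65%–47% to 71%–53% with 8 therapists per arm, depending on method. It is 69%–56% with 12 per arm (t), and 77%–59% with 8 per arm and r = 0.5 (t). None of these ranges should be quoted without its conditions. The 4-point contrast with usual care is not in doubt.

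**What to change.** Keep 492 and change the text of *Sample size calculation*:

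1. Restate the power as about 77% under the printed inputs, or as 80% with at most 13% loss, and say that the test is two-sided.
2. State that therapist clustering was not allowed for. Add a power table for the two 2-point contrasts (CFT-only against CFT-plus-sensor, and usual care against CFT-only), by assumed ICC (for example 0.01, 0.02, 0.05), therapists per arm (8 and 12) and any baseline-outcome correlation the sponsor is prepared to state. Use one method throughout so that the contrasts can be compared.
3. Say whether the SD of 6 is raw or already adjusted for baseline, so that baseline credit is not counted twice.

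The cost is a less favourable stated figure. No patients are added, and neither the design nor the analysis changes.
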